***12.5.10.1.2. Follow-up after the subject is discharged from the study*****The investigator will follow subjects:**

- With SAEs, pIMDs (serious or non-serious), or subjects withdrawn from the study as a result of an AE, until the event has resolved, subsided, stabilized, disappeared, or until the event is otherwise explained, or the subject is lost to follow-up.

If the investigator receives additional relevant information on a previously reported SAE, he/she will provide this information to GSK using a paper/electronic Expedited Adverse Events Report as applicable.

GSK may request that the investigator performs or arranges the conduct of additional clinical examinations/tests and/or evaluations to elucidate as fully as possible the nature and/or causality of the AE or SAE. The investigator is obliged to assist. If a subject dies during participation in the study or during a recognized follow-up period, GSK will be provided with any available post-mortem findings, including histopathology.

## 12.6. Appendix 6: Country-specific requirements

### 12.6.1. Regulatory and ethical considerations

The study will be conducted in accordance with “the Ministerial Ordinance on the Standards for the Conduct of Clinical Trials of Medicinal Products (MHW Notification No.28 dated 27th March, 1997)” and Law for Ensuring the Quality, Efficacy, and Safety of Drugs and Medical Devices.

The statement “I agree to assume responsibility for the proper conduct of the study at this site.” on the Investigator Protocol Agreement Page means the investigator’s responsibility as defined by Japanese GCP.

GSK Japan will submit the CTN to the regulatory authorities in accordance with Law for Ensuring the Quality, Efficacy, and Safety of Drugs and Medical Device before conclusion of any contract for the conduct of the study with study sites.

### 12.6.2. Informed consent

Prior to participation in the study, the investigator (or sub-investigator) should fully inform the potential subject or designee including the written approval given by the IRB. The investigator (or sub-investigator) should provide the subject or designee ample time and opportunity to inquire about details of the study. The subject or designee should sign and personally date the consent form. If the subject wishes to consider the content of the written information at home, he/she may sign the consent form at home. The person who conducted the informed consent discussion and the study collaborator giving supplementary explanation, where applicable, should sign and personally date the consent form. The investigator (or delegator) should retain this signed and dated form (and other written information) together with the source medical records, such as clinical charts (in accordance with the rules for records retention, if any, at each medical institution) and give a copy to the subject or designee

### 12.6.3. Study administrative structure

Sponsor Information and List of Medical Institutions and Investigators are included in Exhibit 1 and Exhibit 2, respectively.

### 12.6.4. Unapproved medical device

If unapproved medical devices are used in the study, further details will be added in Exhibit 3. In case no unapproved medical devices are used, Exhibit 3 will not be attached.

**12.7. Appendix 7: FDA guidance for industry: toxicity grading scale for healthy adult and adolescent volunteers enrolled in preventive vaccine clinical trials (September 2007) - Tables for laboratory abnormalities**

The laboratory values provided in the tables below serve as guidelines and are dependent upon institutional normal parameters. Institutional normal reference ranges should be provided to demonstrate that they are appropriate.

**Table 27 FDA toxicity grading scales for hematology/ biochemistry parameters evaluated in the current study RSV OA=ADJ-003**

Serum *	Mild (Grade 1)	Moderate (Grade 2)	Severe (Grade 3)	Potentially Life Threatening (Grade 4)**
Blood Urea Nitrogen BUN mg/dL	23 – 26	27 – 31	> 31	Requires dialysis
Creatinine – mg/dL	1.5 – 1.7	1.8 – 2.0	2.1 – 2.5	> 2.5 or requires dialysis
Liver Function Tests –ALT, AST increase by factor	1.1 – 2.5 x ULN	2.6 – 5.0 x ULN	5.1 – 10 x ULN	> 10 x ULN

\* The laboratory values provided in the tables serve as guidelines and are dependent upon institutional normal parameters. Institutional normal reference ranges should be provided to demonstrate that they are appropriate.

\*\* The clinical signs or symptoms associated with laboratory abnormalities might result in characterization of the laboratory abnormalities as Potentially Life Threatening (Grade 4).

\*\*\* "ULN" is the upper limit of the normal range.

Hematology *	Mild (Grade 1)	Moderate (Grade 2)	Severe (Grade 3)	Potentially Life Threatening (Grade 4)
Hemoglobin (Female) - gm/dL	11.0 – 12.0	9.5 – 10.9	8.0 – 9.4	< 8.0
Hemoglobin (Female) change from baseline value - gm/dL	Any decrease – 1.5	1.6 – 2.0	2.1 – 5.0	> 5.0
Hemoglobin (Male) - gm/dL	12.5 – 13.5	10.5 – 12.4	8.5 – 10.4	< 8.5
Hemoglobin (Male) change from baseline value – gm/dL	Any decrease – 1.5	1.6 – 2.0	2.1 – 5.0	> 5.0
WBC Increase - cell/mm 	10 800 – 15 000	15 001 – 20 000	20 001 – 25 000	> 25 000
WBC Decrease - cell/mm 	2 500 – 3 500	1 500 – 2 499	1 000 – 1 499	< 1 000
Lymphocytes Decrease - cell/mm 	750 – 1 000	500 – 749	250 – 499	< 250
Neutrophils Decrease - cell/mm 	1 500 – 2 000	1 000 – 1 499	500 – 999	< 500
Eosinophils - cell/mm 	650 – 1 500	1 501 – 5 000	> 5 000	Hypereosinophilic
Platelets Decreased - cell/mm 	125 000 – 140 000	100 000 – 124 000	25 000 – 99 000	< 25 000

\* The laboratory values provided in the tables serve as guidelines and are dependent upon institutional normal parameters. Institutional normal reference ranges should be provided to demonstrate that they are appropriate.

\*\* "ULN" is the upper limit of the normal range.

**LIST OF ABBREVIATIONS**

AE	Adverse event
AESI	Adverse Events of Special Interest
ALT	Alanine Aminotransferase
AS01B:	MPL, QS-21, liposome based Adjuvant System (50µg MPL and 50µg QS-21)
AST	Aspartate Aminotransferase
BUN	Blood Urea Nitrogen
CI	Confidence Interval
CRF	Case Report Form
CSR	Clinical Study Report
CTRS	Clinical Trial Registry Summary
eCRF	Electronic Case Report Form
eDiary	electronic Diary
ELU/mL	ELISA unit per milliliter
Eli Type	Internal database code for type of elimination code
EoS	End of Study
ES	Exposed Set
eTMF	Electronic Trial Master File
GMC	Geometric mean antibody concentration
GMT	Geometric mean antibody titer
GSK	GlaxoSmithKline
HR	Hazard Ratio
IU/mL	International Units per milliLiter
LL	Lower Limit of the confidence interval

Mcg or $\mu$ g	Microgram
MedDRA	Medical Dictionary for Regulatory Activities
NA	Not Applicable
PD	Protocol Deviation
PPS	Per-Protocol Set
RR	Relative Risk
SAE	Serious adverse event
SAP	Statistical Analysis Plan
SBIR	GSK Biological's Internet Randomization System
SD	Standard Deviation
SDTM	Study Data Tabulation Model
SR	Study Report
SUSAR	Suspected Unexpected Serious Adverse Reaction
TFL	Tables Figures and Listings
ToC	Table of Content
UL	Upper Limit of the confidence interval
WBR	Web-based Randomization

## 1. DOCUMENT HISTORY

Date	Description	Protocol Version
23 SEP 2019	First version	Final: 30 APR 2019

## 2. OBJECTIVES/ENDPOINTS

**Table 1** Study objectives and endpoints

[figure not shown]
Objectives	Endpoints
Primary	

 
To evaluate the safety and reactogenicity of 2 doses of the investigational RSV vaccine administered IM according to a 0, 2-month schedule, up to one month after the last dose (Day 91, Visit 6).
 
	
 
Occurrence of AEs from first vaccination up to 30 days after the second vaccination (Day 91): 
 
Occurrence of each solicited local and general AE during a 7-day follow-up period (i.e., on the day of vaccination and 6 subsequent days) after each vaccination.
 
Occurrence of any unsolicited AE during a 30-day follow up period (i.e., on the day of vaccination and 29 subsequent days) after each vaccination.
 
Occurrence of any hematological (erythrocytes, WBC and differential count, platelets count and hemoglobin level) and biochemical (ALT, AST, creatinine, BUN and uric acid) laboratory abnormalities at Days 1, 8, 61 and 68.
 
Occurrence of all Grade 3 non-serious AEs (solicited and unsolicited) during the 30-day follow-up period after each vaccination.
 
Occurrence of SAEs from Dose 1 up to 30 days after the second vaccine dose (Day 91).
 
Occurrence of pIMDs from Dose 1 up to 30 days after the second vaccine dose (Day 91).
 
 
 

Secondary	

 
To evaluate the humoral immune responses of the investigational RSV vaccine administered IM according to a 0, 2-month schedule, up to one month after the last dose (Day 91, Visit 6).
 
To evaluate the safety of 2 doses of the investigational RSV vaccine administered IM according to a 0, 2 -month schedule, up to the end of follow-up (Month 14, Phone call 2).
 
To evaluate the occurrence of RSV-associated respiratory tract infections (RTI) during the RSV seasons in combined nasal and throat swab samples collected during the assessment visit for potential RSV-RTI.
 
	
 
Humoral immune response with respect to components of the investigational vaccine at pre-vaccination (Day 1), 30 days post-Dose 1 (Day 31), on the day of second vaccination (Day 61) and 30 days post-Dose 2 (Day 91): 
 
Neutralizing antibody titers against RSV-A.
 
RSVPreF3-specific IgG antibody concentrations.
 
 
 
Occurrence of SAEs from Dose 1 up to the end of follow-up.
 
Occurrence of pIMDs from Dose 1 up to the end of follow-up.
 
Occurrence of qRT-PCR confirmed RSV-associated RTI in the combined nasal and throat swabs collected during the assessment visit for potential RSV-RTI during the RSV seasons, up to the end of follow-up.
 

Objectives	Endpoints
Tertiary	

 
To further characterize immune responses to investigational RSV vaccine formulation.
 
	
 
Humoral immune response with respect to components of the investigational vaccine at pre-vaccination (Day 1) and 30 days post-Dose 2 (Day 91): 
 
Neutralizing antibody titers against RSV serotype B.
 
 
 
Any further exploratory immunology to detect RSV-related immune responses, such as but not limited to: 
 
Antibodies against specific protein F epitopes.
 
Potential new immunological markers for protection.
 
Cross-reactive neutralizing antibody titers against hMPV.
 
 
 


 
To evaluate the occurrence of RSV-associated RTI during the RSV seasons using self-collected nasal swabs.
 
	
 
Occurrence of qRT-PCR confirmed RSV-associated RTI in self-collected nasal swab samples during the RSV seasons, up to the end of follow-up.
 

IM: intramuscular; RSV: respiratory syncytial virus; AE: adverse event; WBC: white blood cells; ALT: alanine aminotransferase; AST: aspartate aminotransferase; BUN: blood urea nitrogen; SAE: serious adverse event; pIMD: potential immune-mediated disease; RTI: respiratory tract infection; qRT-PCR: quantitative reverse transcription polymerase chain reaction, hMPV: Human metapneumovirus

### 3. STUDY DESIGN

**Figure 1** Study design overview

BS S: Blood sample for safety evaluation (hematology/biochemistry)

BS H: Blood sample for humoral immune responses

qRT-PCR: quantitative reverse transcription polymerase chain reaction

\* Visit 1 should take place no longer than 30 days after the Screening Visit. In case Visit 1 occurs more than 30 days after the Screening Visit, a re-screening visit should be scheduled before Visit 1 during which blood sample collection for safety laboratory assessment must be repeated (maximum one re-screening per subject is allowed). Only

laboratory results from the re-screening visit, if it occurs, will be taken into consideration and recorded in the eCRF. Medical history, physical examination and review of inclusion/exclusion criteria must be repeated if a re-screening visit occurs. The subject can only be randomized once the investigator receives the results and confirms the eligibility criteria.

\*\* An internal Safety Review Committee (iSRC) evaluation of safety data up to Day 8 from all subjects will be performed before proceeding with administration of Dose 2. Additional iSRC evaluations will happen during the conduct of the study.

† In case of RTI symptoms during the RSV seasons (from August until end of February), the subject will be asked to collect a nasal swab at home and contact the investigator/study staff to schedule an assessment visit for collection of an additional nasal swab and a throat swab at the site. The assessment visit should take place as soon as possible after the start of symptoms (ideally within 48 hours, but no later than 7 days).

‡ A first analysis will be performed on all data collected up to Day 91 for at least primary and secondary endpoints (except for the occurrence of RSV RTI). The analysis will be based on data as clean as possible.

- **Type of study:** self-contained.
- **Experimental design:** A phase I, observer-blind, randomized, placebo-controlled, single-country study with 2 parallel groups (see [Figure 1](#)):
- **Duration of the study:** approximately 14 months per subject.
  - Epoch 001: Screening Visit (Day -30 to -3)
  - Epoch 002: Primary (vaccination phase) starting at Visit 1 (Day 1) and ending at Visit 6 (Day 91)
  - Epoch 003: Follow-up starting after Visit 6 (Day 91) and ending at Phone Call 2 (Month 14)
- **Primary Completion Date (PCD):** last visit of the vaccination phase (Visit 6 [Day 91]).
- **End of Study (EoS):** Last testing results released of samples collected up to Phone call 2 (Month 14) (for assays related to secondary endpoints only), or Last subject last Phone Call, whichever comes last.

While no samples will be collected at Phone calls 1 and 2, nasal and throat swabs may be collected in case of RTI symptoms up to the Phone call 2 (Month 14) timepoint, if this timepoint falls within the RSV season.
- **Study groups:**
  - **RSV Group:** subjects receiving 2 doses of the investigational RSV vaccine containing 120 µg RSVPreF3 adjuvanted with AS01B.
  - **Placebo:** subjects receiving 2 doses of placebo as control.
- **Vaccination schedule:** Two vaccine doses administered intramuscularly at Day 1 and Day 61.
- **Treatment allocation:** Subjects will be randomized using a centralized randomization system on internet (SBIR) on Day 1.

A total of approximately 40 participants are planned to be enrolled in this study in a 1:1 ratio. The target is to enrol approximately 28 eligible participants aged 60-69 years (approximately 14 per group) and approximately 12 (and minimum 10) eligible participants aged 70-80 years (approximately 6 per group). The randomization algorithm will use a minimization procedure accounting for age, center and gender.

- **Blinding:** observer-blind.

The vaccination phase (Epoch 002) will be observer-blind. A first statistical analysis will be performed on data available up to one-month post-Dose 2 (Visit 6, Day 91). Given that summary safety results may unblind some specific subjects, the follow-up phase (Epoch 003) will be considered as single-blind with subjects remaining blinded up to study end (Phone Call 2 [Month 14]). The investigators will not be provided with the individual data listings or with the randomization listings until the end of study analysis.

- **RTI surveillance:** Active and passive surveillance will only be carried out during RSV seasons (from August until end of February) throughout the entire study:

- Active surveillance: study participants will be contacted by the investigator/study staff every 2 weeks to identify if they experienced an RTI.
- Passive surveillance: study participants are instructed to contact the investigator/study staff as soon as they experience an RTI.

At the beginning of the RSV season, study participants will be reminded of the start of the RTI surveillance.

- **Safety monitoring:** The study will be conducted with oversight by an internal Safety Review Committee (iSRC). An iSRC evaluation of safety data up to Day 8 from all subjects will be performed before proceeding with administration of Dose 2. The investigator is not permitted to start the administration of the next dose until receipt of the favourable outcome of the safety evaluation by the iSRC. A second data review iSRC meeting will be held to review all available safety data up to 30 days post-Dose 2. During the follow-up phase, 2 iSRC meetings will be planned with an interval of approximately 6 months.

- **Group description for analysis**

For the analysis by age category, the following sub-group names will be used in the TFLs

Sub-group label in tables	Sub-group definition for footnote
60-69Y	60 to 69 years old subjects
70-80Y	70 to 80 years old subjects

## 4. ANALYSIS SETS

### 4.1. Definition

For purposes of analysis, the following analysis sets are defined:

Analysis Set	Description
Enrolled	All subjects who sign informed consent.
Exposed	All subjects who received at least 1 dose of the study treatment. The allocation in a group is done in function of the administered treatment.
Per Protocol	All subjects who received at least 1 dose of the study treatment to which they are randomized and have post-vaccination data minus subjects with protocol deviations that lead to exclusion.

### 4.2. Criteria for eliminating data from Analysis Sets

Elimination codes are used to identify subjects to be eliminated from analysis. Detail is provided below for each set.

#### 4.2.1. Elimination from Exposed Set (ES)

Code 1030 (Study vaccine not administered at all), 800 (Fraudulent data) and code 900 (invalid informed consent or other GCP noncompliance) will be used for identifying subjects eliminated from ES.

#### 4.2.2. Elimination from Per-protocol analysis Set (PPS)

##### 4.2.2.1. Excluded subjects

A subject will be excluded from the PPS analysis under the following conditions

- For codes 800, 900, 1030, 1050 and 1060: subjects will be eliminated for all visits.
- For codes 1040, 1070, 1080, 1090, 2010, 2040, 2060, 2080: subjects will be eliminated from a specific visit (at which the condition is met) onwards.
- For codes 2090, 2100, 2120: subjects will be eliminated for the specific visit at which the condition is met.

Code	Condition under which the code is used	Visit (timepoints) where the code is applicable	Applicable for analysis set
800	Fraudulent data	All	ES and PPS for analysis of immunogenicity
900	Invalid informed consent or other GCP non-compliance	All	ES and PPS for analysis of immunogenicity
1030	Study vaccine not administered at all	All	ES and PPS for analysis of immunogenicity
1040	Administration of concomitant vaccine(s) forbidden in the protocol Any investigational or non-registered vaccine other than the study vaccine used during the study period	All	PPS for analysis of immunogenicity

Code	Condition under which the code is used	Visit (timepoints) where the code is applicable	Applicable for analysis set
	A vaccine not foreseen by the study protocol administered during the period starting 30 days before the first dose and ending 30 days after the last vaccine dose, except for inactivated and subunit influenza vaccines which can be administered up to 14 days before or from 30 days after each vaccination.		
1050	Randomization failure	All	PPS for analysis of immunogenicity
1060	Randomization code was broken	All	PPS for analysis of immunogenicity
1070	Vaccination not according to protocol Incomplete vaccination course Subject was vaccinated with the correct vaccine but containing a lower volume Wrong replacement or study vaccine administered (not compatible with the vaccine regimen associated to the treatment number) Route of the study vaccine is not intramuscular Wrong reconstitution of administered vaccine	Vaccination visits 1 and 4	PPS for analysis of immunogenicity
1080	Vaccine temperature deviation Vaccine administered despite a Good Manufacturing Practices (GMP) no-go temperature deviation	Vaccination visits 1 and 4	PPS for analysis of immunogenicity
1090	Expired vaccine administered	Vaccination visits 1 and 4	PPS for analysis of immunogenicity
2010	Protocol violation (inclusion/exclusion criteria)	All	PPS for analysis of immunogenicity
2040	Administration of any medication forbidden by the protocol Any investigational or non-registered medication used during the study period Immunosuppressants or other immune-modifying drugs administered chronically (i.e., more than 14 consecutive days in total) during the study period Long-acting immune-modifying drugs administered at any time during the study period Immunoglobulins and/or any blood products administered during the study period	All	PPS for analysis of immunogenicity
2060	Intercurrent medical condition Subjects may be eliminated from the PPS if, during the study, they incur a condition that has the capability of altering their immune response or are confirmed to have an alteration of their initial immune status (other than RSV infection).	All	PPS for analysis of immunogenicity
2080	Subjects did not comply with vaccination schedule number of days between dose 1 and dose 2 is outside [55-65 days]	Visit 4	PPS for analysis of immunogenicity

Code	Condition under which the code is used	Visit (timepoints) where the code is applicable	Applicable for analysis set
2090	Subjects did not comply with blood sample schedule Number of days between dose 1 and visit 3 blood sample is outside [30-37 days] Number of days between dose 2 and visit 6 blood sample is outside [30-37 days]	Visits 3 and 6	PPS for analysis of immunogenicity
2100	Serological results not available post-vaccination No immunological result at visit x for all 2 following tests: RSV A Neutralising antibody titer and RSVPreF3-specific IgG antibody concentration	Visits 3, 4, 6	PPS for analysis of immunogenicity
2120	Obvious incoherence or abnormality or error in data Unreliable released data as a result of confirmed sample mismatch or confirmed inappropriate sample handling at lab	Visits 1, 3, 4, 6	PPS for analysis of immunogenicity

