**7.3. Blinding and unblinding**

During the vaccination phase, data will be collected in an observer-blind manner. By observer-blind, it is meant that during the course of the study, the vaccine recipient and those responsible for the evaluation of any study endpoint (e.g. safety and reactogenicity) will all be unaware of which vaccine was administered. To do so, vaccine preparation and administration will be done by authorized medical personnel who will not participate in any of the study clinical evaluation assays.

A first statistical analysis will be performed on data available up to one-month post-Dose 2 (Visit 6, Day 91) (See Section 10.4 for details on the sequence of analyses). Given that summary safety results may unblind some specific subjects (e.g. an AE occurring only in a single group), anyone having access to this first analysis could become unblinded regarding that specific case. Therefore, the follow-up phase (Epoch 003) will be considered as single-blind with subjects remaining blinded up to study end (Phone call 2 [Month 14]). The investigators will not be provided with the individual data listings or with the randomization listings until the end of study analysis.

The laboratory in charge of the laboratory testing will be blinded to the treatment, and codes will be used to link the subject and study (without any link to the treatment attributed to the subject) to each sample.

GSK's policy (which incorporates ICH E2A guidance, EU Clinical Trial Directive and US Federal Regulations) is to unblind the report of any SAE which is unexpected and attributable/suspected to be attributable to the study vaccine, prior to regulatory reporting. The GSK Central Safety Physician is responsible for unblinding the treatment assignment in accordance with the specified timeframes for expedited reporting of SAEs (refer to Section 12.5.8.1).

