### 7.3.1. Emergency unblinding

Unblinding of a subject's individual treatment code should occur only in the case of a medical emergency when knowledge of the treatment is essential for the clinical management or welfare of the subject.

The emergency unblinding process consists of the automated Internet-based system (SBIR) that allows the investigator to have unrestricted, immediate and direct access to the subject's individual study treatment.

As back up process, the investigator has the option of contacting a GSK Helpdesk (refer to [Table 6](#)) if he/she needs support to perform the unblinding (i.e. he/she cannot access the automated Internet-based system).

Non-investigator physician (e.g. physician from emergency room) or subject/care giver/family member can also request emergency unblinding either via the investigator (preferred option) or via the GSK Helpdesk (back up process). Contact details of investigator and GSK Helpdesk are reported in the patient/subject card.

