**Table 6 Contact information for emergency unblinding**

GSK Helpdesk 24/24 hour and 7/7 day availability
The Helpdesk is available by phone, fax and email Phone: PPD Fax: PPD email: PPD

A subject may continue in the study if that subject's treatment assignment is unblinded.

GSK Vaccines Clinical Safety and Pharmacovigilance (VCSP) staff may unblind the treatment assignment for any subject in case of Suspected Unexpected Serious Adverse Reaction (SUSAR) as well as in case of fatal or life-threatening cases. If the SAE requires that an expedited regulatory report be sent to 1 or more regulatory agencies, a copy of the report, identifying the subject's treatment assignment, may be sent to investigators in accordance with local regulations and/or GSK policy.

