## **7. CONDUCT OF ANALYSES**

### **7.1. Sequence of analyses**

The following analyses will be performed stepwise:

- A first analysis will be performed on all data available and as clean as possible, when data for at least primary and secondary endpoints up to Day 91 are available (except for the occurrence of RSV RTI). This analysis will be considered as final for those endpoints. A statistical report will be written.

At this point, the statistician will be unblinded (i.e., individual subject treatment assignments will be available), but no individual listings will be provided to the study team. Given that summary safety results may unblind some specific subjects, the study will be considered as single-blind from this point onwards, with subjects remaining blinded up to study end (Month 14). The investigators will not be provided with the individual data listings or with the randomization listings until the end of study analysis.

- The end of study analysis will be performed when all data for primary and secondary endpoints up to study conclusion are available (Month 14). Individual listings will only be provided at this stage. An integrated clinical study report containing all available data will be written and made available to the investigators.

The final study report will contain at least the final analyses of all primary and secondary endpoints. If the data for tertiary endpoints become available at a later stage, (an) additional analysis/ analyses will be performed. These analyses will be documented in annex(es) to the study report and will be made available to the investigators at that time.

Description	Analysis ID	Disclosure Purpose (CTRS=public posting, SR=study report, internal)	Reference for TFL TOC
End of study analysis	E1_01	CTRS, SR	See column 5 in TFL TOC
Analysis up to Day 91	E1_02	Internal	See column 5 in TFL TOC

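### SAP code 1060 (broken randomization code) carries no date limit, so on the literal text a break after Visit 6 excludes earlier, unaffected antibody results from the per-protocol set

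*SAP*

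**What the plan says.** SAP 4.2.2.1 sorts the elimination codes by reach. The first group is: "For codes 800, 900, 1030, 1050 and 1060: subjects will be eliminated for all visits". Code 1060 is described only as "Randomization code was broken"; its table row lists all timepoints and applies it to the immunogenicity PPS. The row does not say who broke the code, why, or when. For a second group, which includes forbidden vaccines (1040), forbidden medication (2040) and intercurrent conditions (2060), "subjects will be eliminated from a specific visit (at which the condition is met) onwards".

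Other relevant provisions:

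- **Exposed Set.** SAP 4.2.1 names codes 1030, 800 and 900, which "will be used for identifying subjects eliminated from ES". Code 1060 is not among them.
- **Use of the sets.** SAP 5.3 makes the PPS primary for immunogenicity. It adds an Exposed Set analysis if, in any group at any timepoint, at least 10% of vaccinated subjects with serology are excluded.
- **Unblinding.** Protocol 7.3.1 states: "Unblinding of a subject's individual treatment code should occur only in the case of a medical emergency". It adds that sponsor safety staff "may unblind the treatment assignment for any subject in case of Suspected Unexpected Serious Adverse Reaction (SUSAR"), and likewise in fatal or life-threatening cases. No time limit is set, and an unblinded subject may stay in the study.
- **Timing.** Antibody samples are taken on Days 1, 31, 61 and 91 (Protocol 5.2). SAEs are collected until 12 months after the last dose (Protocol 12.5.7.1).
- **Assay blinding.** Protocol 7.3: "The laboratory in charge of the laboratory testing will be blinded to the treatment".
- **First analysis.** SAP 7.1 says of the Day 91 analysis: "This analysis will be considered as final for those endpoints". That analysis is labelled internal; public posting and the study report use the end-of-study analysis.

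**The concern.** The other codes in the all-visits group describe defects that are present from the start or that taint the whole record: fraud, invalid consent or GCP non-compliance, no vaccination, randomization failure. A code break happens on a date. The SAP handles other dated events, such as a forbidden drug or an intercurrent condition, from that visit onwards. Code 1060 is the exception, and no reason is given.

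A serum sample drawn before the break and assayed by a blinded laboratory cannot be influenced by it, so backward exclusion removes no bias. It may introduce some. If safety unblinding counts as a code break, a subject's place in the primary immunogenicity set at Day 31 could depend on a serious event months later that was suspected to be vaccine-related. The end-of-study antibody summaries could then also differ from those declared final at Day 91.

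**Working it through.** **Plan's own figures.** The plan gives no figure for this rule. Its sample-size statement (Protocol 10.1.1, 20 per group) reproduces: 1 − (1 − 0.078)^20 = 0.803 and 1 − (1 − 0.109)^20 = 0.901, against the stated 80% and 90%. Protocol 5.3 allows 10% non-evaluable: 40 × 0.9 = 36, or 18 per arm. I therefore use arms of 18 to 20.

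**Which results the rule reaches.** Assume that the break is coded 1060 and falls after Visit 6.

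| Rule | Antibody timepoints lost |
|---|---|
| As written (all visits) | 4 of 4 (Days 1, 31, 61, 91) |
| From the break onwards | 0 of 4 |

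**When this changes a result.**

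1. Break after the subject's own Visit 6 but before the first analysis: the exclusion is in force when the PPS is first derived, so the effect is certain.
2. Break after the first analysis: the Day 91 results are already final. They change only if the PPS is re-derived for the end-of-study analysis, and the SAP does not say whether it is.
3. Tertiary RSV-B titres (Days 1 and 91) may be analysed later still under SAP 7.1, so a break before that analysis can reach them.

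**Share of an arm and the 10% trigger.**

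- One subject: 1/20 = 5.0%, 1/18 = 5.6%. Not triggered if it is the only exclusion.
- Two subjects: 2/20 = 10.0%, 2/18 = 11.1%. Triggered. The second exclusion may be for any reason.

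**Precision.** On the log scale, the half-width of a 95% CI for a GMT or GMC is t(0.975, n − 1) × s/√n. Holding s fixed:

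| n before → after | Half-width (units of s) | Widening |
|---|---|---|
| 20 → 19 | 0.468 → 0.482 | 3.0% |
| 18 → 17 | 0.497 → 0.514 | 3.4% |
| 20 → 18 | 0.468 → 0.497 | 6.3% |
| 18 → 16 | 0.497 → 0.533 | 7.2% |

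**How often (assumption).** The documents give no unblinding rate. With a per-subject rate r during follow-up, P(at least one among 40) = 1 − (1 − r)^40, and P(two or more in one arm of 20) = 1 − (1 − r)^20 − 20r(1 − r)^19.

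| r | At least one of 40 | Two or more in one arm |
|---|---|---|
| 0.5% | 18% | 0.4% |
| 1% | 33% | 1.7% |
| 2% | 55% | 6.0% |
| 5% | 87% | 26% |

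Across most of this range, if the problem arises at all, it is as a single case in an arm. That is the case the 10% trigger does not expose on its own.

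**The case against.** On the other side, the following can fairly be said.

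- **The Day 91 results are final.** A reader might infer that any unblinding in follow-up retroactively deletes valid Day 1-91 results. The documents do not support that. SAP 7.1 declares the first analysis final for those endpoints, so a later break matters only if the PPS is rebuilt. This stands and limits the point, but does not remove it: the SAP does not say that the PPS is frozen, and what is published comes from the end-of-study analysis.
- **Nothing is deleted.** Code 1060 leaves the subject in the Exposed Set, and an Exposed Set immunogenicity analysis follows once exclusions reach 10%. This stands, except that one exclusion alone does not trigger that analysis.
- **Safety unblinding may not be a code break.** A reader might infer that every SUSAR unblinding triggers code 1060. No text says so. Unblinding under Protocol 7.3 and 7.3.1 is permitted rather than a deviation, and follow-up is single-blind by design, so the code may be meant for breaks of the observer-blind phase. This is plausible but unwritten. It is a reason to define the code's scope.
- **The effect on the GMT is speculative.** If the lost subject's titre were 10-fold the geometric mean of the others, the GMT would move by 12-14% (10^(1/20) = 1.122; 10^(1/18) = 1.136). A 2-fold difference gives 3.5-3.9% (2^(1/20) = 1.035; 2^(1/18) = 1.039). Neither multiple comes from the documents, so I do not rest the point on them.
- **No decision hangs on it.** The antibody endpoints are secondary or tertiary, and SAP 6 makes all analyses descriptive. This stands, and it keeps the priority low.

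**Conclusion.** The point holds in a limited form. As written, SAP 4.2.2.1 excludes from the PPS antibody results collected before a code break, although the break cannot have affected them. This is certain for a break after the subject's own Visit 6 and before the first analysis. For later breaks it depends on whether the PPS is re-derived for the end-of-study or later RSV-B analyses, which the SAP leaves open.

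The size is modest: 5.0-5.6% of an arm and CIs about 3% wider per subject lost, with the log-scale SD held constant. Few events are expected (0 to 2 in 40, an assumption). The conclusion rests on a literal reading of the code and on the break being recorded as 1060. The documents do not establish that results are lost from the trial, that safety unblinding always triggers the code, or that the GMT would move by any particular amount. This is a free improvement rather than a flaw that threatens the trial's conclusions.

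**What to change.** In SAP 4.2.2.1, move code 1060 from the all-visits list to the list that eliminates from the visit concerned onwards, and align its table row. Because a break need not coincide with a visit, tie the start to the date of the break, so that samples drawn before it stay in the PPS.

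Add two sentences:

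1. whether sponsor safety unblinding, as distinct from emergency unblinding by the investigator, triggers code 1060;
2. whether the immunogenicity PPS is frozen at the Day 91 analysis or re-derived for the end-of-study and later tertiary analyses.

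The move alone settles breaks after Visit 6. Breaks during the vaccination phase would still exclude later visits, and the first sentence would make clear which breaks count.

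The cost is a few lines of SAP text, with no change to conduct, data collection or sample size. It should be done before the PPS is first derived.
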